7.1.3 Active Phase 1 Month (± 3 days), or VA2

The first 24 subjects randomized will return to the clinic at 1 Month (± 3 days) for a complete safety assessment including a physical examination, a review of concomitant medication and diseases, AEs, and clinical labs. Efficacy scales/scores will also be completed by the subject, and assisted by physician (as needed), and at least 4 patients from each group will be represented. All required assessments at 1-month follow-up are outlined in Appendix A.

7.1.4 Conservative Treatment Group 3 Months (± 14 days), or VA3

Patients randomized to the conservative arm will be evaluated with VASPI, ODI, SF-36 questionnaires as well as complete all required additional assessments as outlined in Appendix A during the 3 months visit. Patients will be evaluated for deteriorating or improving conditions relative to enrollment. Subjects who have experienced a significant decline in condition defined as a 10% increase in pain by VASPI, or a 9-point increase in ODI will be offered the allograft treatment as a crossover. If the subject does not meet the aforementioned changes in ODI or VASPI, or is considering withdrawal, they may also be offered the allograft treatment by physician discretion if condition has significantly declined. Subjects that crossover do not have to re-consent. The crossover allograft treatment can occur at any time period after the 3-month follow-up visit. To administer the crossover allograft treatment, a new visit will be scheduled and this visit will be considered as the new Active Phase Day 0. In addition to the 3 months follow-up visit assessments, these crossover subjects will receive a MRI and X-ray prior to the allograft treatment. All assessments done at this 3 months follow-up visit will be considered as the new baseline assessments. These crossover subjects will receive follow-up visits at 6 months and 12 months after allograft treatment. Crossover subjects will not be replaced by enrolling new patients in the conservative care treatment group.

7.1.5 Active Phase Month 6 (± 30 days) or VA4:

All randomized subjects will return to the clinic 6 months (± 30 days) subsequent to treatment for all safety and efficacy assessments as outlined in Appendix A. ODI, VASPI, and SF-36 questionnaires will be completed by the subject, and assisted by physician or physician designee. All subjects (excluding conservative care crossover subjects) will be randomized to include MRI at 6-month (MRI or no MRI, ratio 1:1) follow-up in addition to all other assessments. This randomization is performed to assess whether predictability at 6 months indicates performance at 12 months. The conservative care subjects that crossover to the allograft treatment group will all receive an MRI at 6-month follow-up after allograft treatment. All subjects will receive an X-ray at the 6-month follow-up visit. Additionally, a review of resource utilization since the Day 0 visit will be completed.

CONFIDENTIAL	Clinical Protocol	DATE	Р	age
		9Dec2019		T
TITLE: V iable A llograft S upplemented Disc Regeneration in the T reatment of		WRITER TG, DB, PW	NO.	REV
Patients with Low Back Pain with VAST-001-017	th or without Intervertebral Disc Herniation –	. 0, 22,	31	6

7.1.6 Active Phase Month 12 (+ 30 days) or VA5:

All randomized subjects will return to the clinic 12 months (+ 30 days) subsequent to transplantation for safety and efficacy assessments as outlined in Appendix A. ODI, VASPI, and SF-36 questionnaires will be completed by the subject, with assistance from physician or physician designee. All subjects will receive an MRI and X-ray at the 12-month follow-up visit. A review of resource utilization through the 12 Month visit will be completed.

7.1.7 Optional Long-Term Follow Up Month 24 & Month 36 (+ 3 Months) or VA6 & VA7:

All randomized subjects will have an option to continue to be monitored for long-term follow up. Before study procedures begin, the informed consent addendum 2 for study extension will need to be signed. At the 24-month in-office visit, subjects will first be reevaluated for inclusion/exclusion and fill out VASPI, ODI, SF-36, and Resource Utilization. If eligible for allograft treatment, the PI will perform a neurological exam, physical exam, labs, and give the subject applicable questionnaires. All randomized subjects will have the option to receive allograft treatment at 24 months in accordance with the inclusion/exclusion re-evaluation. An MRI and x-ray will be performed on subjects receiving another injection for safety purposes. If needed, a second office visit may be scheduled within 14 days of the original evaluation to allow appropriate time for the laboratory investigation and MRI. All follow up subjects will complete VASPI, ODI, SF-36, and Resource Utilization questionnaires at both follow up visits. The 36-month will consist of questionnaires and can be performed over the phone if the subject chooses.

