APPENDIX A - STUDY SCHEDULE

Visit	VS1 ^a	VA1 ^a	VA2 ^b	VA3 ^c	VA4	VA5	VA6	VA7
Visit Window	Screening (Day -14 to 0)	Day 0	1 month (±3 Days)	3 months (±14 Days)	6 months (± 30 Days)	12 months (+ 30 Days)	24 months (± 3 Months)	36 months (± 3 Months)
Informed Consent	Х						Х	
Eligibility Criteria	Х							
Eligibility Criteria Check		Х					х	
Randomization		Х						
Injection Treatment (Allograft or Saline)		Х					X ^f	
Demographic Data	х							
Medical History	х							
Physical Examination		Х	х	Х	Х	Х	X ^f	
Neurological Examination		Х	Х	X	X	X	Χ ^f	
MRI and X-ray Evaluations	X		X	X ^d	X e	X	X ^f	
Laboratory Investigation	Х		Х	Х	Х	Х	X ^f	
Urine/Pregnancy Test, if applicable		Х						
VASPI Questionnaire	х		х	Х	х	х	х	Х
SF-36 Questionnaire	x		х	х	х	х	х	x
ODI Questionnaire	х		х	Х	х	х	х	х
Resource Utilization	Х				Х	Х	Х	Х
Concomitant Medication	Х	Х	Х	Х	Х	Х	Х	Х
Adverse Events		Х	х	Х	Х	Х	Х	Х

^a VS1 and VA1 may both occur on Day 0.

^b Month 1 Visit (VA2*) to be performed for the first 24 subjects randomized only.

CONFIDENTIAL	Clinical Protocol	DATE 9Dec2019	Pa	ige
	mented Disc Regeneration in the $\underline{\mathbf{T}}$ reatment of th or without Intervertebral Disc Herniation –	WRITER TG, DB, PW	NO. 57	REV 6

^c Subjects randomized to conservative care will be evaluated at 3 months to assure they are not experiencing further debilitating changes. During this visit, subjects may be offered crossover to allograft treatment. To administer the crossover allograft treatment, a new visit will be scheduled and this visit will be considered as the new Active Phase Day 0 (VA1).

^d MRI and X-ray to be done in the event a subject crosses over from conservative care to the Allograft treatment.

^e At the 6-month follow-up visit, subjects will be randomized to receive a MRI, (1:1 ratio). Crossover subjects to allograft treatment will all receive an MRI at the 6 month visit after allograft treatment. All subjects will receive an X-ray at the 6 month follow up visit.

f At the 24-month in-office visit, subjects will first be reevaluated for inclusion/exclusion and fill out VASPI, ODI, SF-36, and Resource Utilization. If eligible for allograft treatment, the PI will perform a neurological exam, physical exam, laboratory investigation, and MRI/X-ray.

[figure not shown]
CONFIDENTIAL	Clinical Protocol DATE		Page	
99111 12 E111111 12		9Dec2019		

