6.2 MODIFIED INTENT TO TREAT POPULATION (MITT)

The modified intent-to-treat population (mITT) includes all ITT subjects who underwent treatment and had at least one valid post-treatment assessment of the ODI and VASPI. This mITT population is the primary analysis population for efficacy analyses. Subjects are analyzed under the treatment to which they were randomized.

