9.1 CO-PRIMARY EFFICACY ENDPOINTS

The co-primary endpoints are the change in ODI and VASPI at 12 months after treatment.

The hypothesis for the ODI is as follows:

H₀: $\tilde{x}_1 = \tilde{x}_2 = \tilde{x}_3$ H_a: at least one median is not equal

Where \tilde{x}_1 is the median pre-post difference in the active allograft group, \tilde{x}_2 is the median pre-post difference in the placebo group and \tilde{x}_3 is the median pre-post difference in the conservative care group.

The null hypothesis (H_0) for this endpoint states that there is no difference in change in ODI at 12 months between the three treatment groups (1) Active Allograft, (2) Placebo, and (3) Conservative Care. The alternative hypothesis (H_a) is that there is a difference in change in ODI at 12 months between the three treatment groups.

The hypothesis for the VASPI is as follows:

 $\begin{array}{l} H_0: \ {\tilde x}_1 = {\tilde x}_2 = {\tilde x}_3 \\ H_a: \ at \ least \ one \ median \ is \ not \ equal \end{array}$

Where \tilde{x}_1 is the median pre-post difference in the active allograft group, \tilde{x}_2 is the median pre-post difference in the placebo group and \tilde{x}_3 is the median pre-post difference in the conservative care group.

The null hypothesis (H₀) for this endpoint states that there is no difference in change in VASPI at 12 months between the three treatment groups (1) Active Allograft, (2) Placebo, and (3) Conservative Care. The alternative hypothesis (H_a) is that there is a difference in change in VASPI at 12 months between the three treatment groups.

For both the ODI and the VASPI, the pre-post difference of the groups will be compared using the Kruskal-Wallis test at a two-sided α -level of 0.05. If the result for either test is significant, then the Dwass, Steel, Critchlow-Fligner Method will be used to assess all pairwise comparisons for that endpoint.

Both the ODI and the VASPI need to be statistically significant (p<0.05) for the trial to be a success.

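### The SAP sets no baseline or visit for conservative-care patients who cross to allograft; using the protocol's reset baseline in the as-randomised analysis would bias that comparison against allograft

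*Protocol*

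**What the plan says.** Protocol 7.1.4 offers allograft to conservative-care patients who worsen by month 3. The trigger is a 10% rise in VASPI or "a 9-point increase in ODI will be offered the allograft treatment as a crossover"; physician discretion is a third route. On timing, "The crossover allograft treatment can occur at any time period after the 3-month follow-up visit", and the injection visit becomes a new Day 0. On baseline, "All assessments done at this 3 months follow-up visit will be considered as the new baseline assessments". On follow-up, "These crossover subjects will receive follow-up visits at 6 months and 12 months after allograft treatment".

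SAP 6.2 defines the primary efficacy population and adds: "Subjects are analyzed under the treatment to which they were randomized". In SAP 9.1, "The co-primary endpoints are the change in ODI and VASPI at 12 months after treatment", and "the pre-post difference of the groups will be compared using the Kruskal-Wallis test", followed by Dwass-Steel-Critchlow-Fligner (DSCF) pairwise comparisons if the overall test is significant.

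The SAP summary mentions month-3 access to allograft and places baseline ODI and VASPI in the screening phase. It does not say whether that baseline still holds after a crossover. SAP 7.3 (missing data), 11.1 (analysis by treatment received) and 13 (changes to the planned analysis) give no crossover rule. The SAP, approved 30 January 2020, cites the protocol issued 11 May 2018. The protocol supplied is Rev 6, dated 9 December 2019.

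**The concern.** For a crossover patient, three terms in SAP 9.1 are undefined: the pre score (screening or month 3), the post score (12 months from the original Day 0 or from allograft), and the treatment from which the 12 months run. The primary outcome cannot be computed for these patients without a choice, and nothing stops that choice being made after the data are seen.

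The one rule written specifically for these patients is the reset in Protocol 7.1.4. Combined with the as-randomised rule, it discards the worsening that occurred on conservative care and counts recovery after allograft as conservative-care improvement. Because patients are selected for a high month-3 score, part of that recovery would be regression to the mean. At stake is the comparison with conservative care, on which Protocol section 6 says the trial's outcomes will be based, and the Kruskal-Wallis test that defines success, which has no direction.

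**Working it through.** **Inputs.** From the documents: allocation 140:40:40, SD 15.5, difference of interest 9 points (SAP 4), ODI trigger 9 points (Protocol 7.1.4), two-sided alpha 0.05. Not in the documents, so assumed: crossover share f of 10%, 25% or 50% (4, 10 or 20 of 40), a reset of d = 9 points for every crossover, and normal change scores.

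**The plan's own figure.** P(x<y) = Φ(−9/(15.5·√2)) = 0.341, as stated. The stated 80% two-sided power with 40 per group does not reproduce (69% by Noether's formula, 70% by simulation). That is a separate matter. At the planned 140 versus 40, two-sided pairwise power is 87–90%, so the work below uses the actual allocation.

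**Identity.** Let B0 be the screening score, B3 the month-3 score and Y the follow-up score, with improvement positive. Then B3 − Y = (B0 − Y) + (B3 − B0). The reset adds d = B3 − B0, at least 9 for anyone who meets the ODI trigger. A patient who goes from 40 (the ODI entry floor) to 49 and back to 40 has improved by 0 from the original baseline and by 9 from the reset one.

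**Expected allograft minus conservative-care difference,** if crossovers gain the full 9 points: 9(1−f) with the original baseline and 9(1−f) − f·d with the reset. At 25%: 6.75 against 6.75 − 2.25 = 4.5. At 50%: 4.5 against 4.5 − 4.5 = 0.

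**Simulation** (20,000 trials per cell; DSCF critical |z| 2.344, applied only if Kruskal-Wallis p<0.05). The last four rows assume a true 9-point effect and give the power of the gated DSCF test to show allograft better than conservative care. In Case A crossovers only return to their original score; in Case B they also gain 9 points.

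| | No crossover | 10% | 25% | 50% |
|---|---|---|---|---|
| No true effect, reset: Kruskal-Wallis rejection | 5% | 5.7% | 9.5% | 26% |
| No true effect, reset: DSCF puts conservative care above allograft | 0.9% | 1.8% | 4.9% | 19% |
| Case A, original baseline | 78–79% | 78% | 79% | 79% |
| Case A, reset | 78–79% | 68% | 49% | 21% |
| Case B, original baseline | 78–79% | 68% | 49% | 21% |
| Case B, reset | 78–79% | 56% | 20% | <1% |

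With no true effect, the original baseline keeps Kruskal-Wallis rejection at about 5% throughout. With a true effect, omnibus power stays at 81% or more and allograft over placebo at 77–78%.

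**Both endpoints together** (no true effect; assumed correlation between endpoints 0.3–0.7). Without a reset, both are significant in 0.4–1.5% of trials. If VASPI carries the same standardised shift as ODI (9/15.5 = 0.58 SD), the figures are 0.5–1.9%, 1.7–3.9% and 10–15% at 10%, 25% and 50% crossover. If the VASPI reset is 4 mm (10% of the 40 mm entry floor) with an assumed SD of 25 mm, the 50% figure is about 2.4–4.5%. The documents give no VASPI SD.

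**The case against.** The strongest reply is that no document puts the reset baseline into the primary analysis. The SAP summary sets baseline in screening and SAP 6.2 analyses as randomised; together they point to the original baseline, under which type I error is not inflated and only ordinary dilution remains. The protocol also speaks of crossing into the allograft group, which could mean a separate cohort, although that conflicts with SAP 6.2. This stands in part: a reader might infer that the plan adopts a biased baseline, and it does not say so. But the summary's statement is general, Protocol 7.1.4 is specific to these patients and says otherwise, and neither text yields to the other. The SAP cites an older protocol that is not supplied, so whether its authors had the reset sentence before them is unknown.

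Second, success needs both endpoints, so the effect on the trial decision is smaller than the per-endpoint error suggests. This stands. A reader might take the 26% as the false-success rate, but it is the ODI test alone. The joint rate exceeds 5% only at 50% crossover with a large VASPI shift that the documents do not support.

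Third, a reader of Appendix A might infer that no ODI or VASPI is taken at the crossover Day 0, since its VA1 column schedules neither. Protocol 8.5 collects self-assessments at every scheduled clinic visit, and 7.1.2 requires baseline questionnaires to be complete at Day 0 while deferring to Appendix A. The texts conflict, so nothing here relies on that absence.

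Fourth, patients who cross on VASPI or by physician discretion need not have worsened by 9 ODI points. This stands; the 9-point reset for every crossover is a simplification.

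**Conclusion.** The concern holds as a gap with a conditional bias. The SAP does not define the primary outcome for a group of patients that the protocol itself creates. Applying Protocol 7.1.4 literally alongside SAP 6.2 biases the conservative-care comparison against allograft by the dropped worsening. The direction follows from the identity; the size depends on the crossover share and on d, neither of which the documents give. On the stated assumptions the effect is slight at 10% crossover. At 25% it is material: Kruskal-Wallis type I error of 9–10% on ODI, and power of 49% instead of 78–79% (Case A) or 20% instead of 49% (Case B).

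The documents do not support two stronger readings: that the trial's main success criterion is broadly invalid, or that the placebo comparison is compromised. Placebo patients can receive allograft only at 24 months, so as-randomised allograft versus placebo at 12 months is untouched. Severity: should fix.

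**What to change.** - In SAP 9.1, state that the as-randomised primary analysis uses change from the original screening baseline for every patient, and that the new baseline of Protocol 7.1.4 does not apply there.
- Before database lock, name the visit that crossovers contribute, anchored to the original Day 0, and say how scores taken after allograft are handled. More than one rule is defensible; it must be written down.
- Report changes from the reset baseline only as a separate descriptive crossover cohort. Do not pool them with randomised changes, including in SAP 11.1.
- Enter the rule in SAP 13 and reconcile it with Protocol Rev 6, including whether ODI and VASPI are collected at the crossover Day 0 (Protocol 7.1.2 and 8.5 against Appendix A).

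The cost is SAP wording and a little programming; the crossover rule is unchanged and no visits are added. Some scores will be off schedule: an injection at month 3 puts the later visits at months 9 and 15 from the original Day 0 (3 + 6 and 3 + 12). If crossovers do benefit, the original baseline still leaves ordinary dilution (49% power at 25% crossover, Case B). The fix removes only the bias added by the reset.

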15.5	Site Initiation	49
15.6	Monitoring	50
15.7	Required Reports	50
16	STUDY REQUIREMENTS	52
16.1	Quality Assurance	52
16.2	Monitoring	53
17	PROCEDURES AND INSTRUCTIONS	55
17.1	Special safety-related procedures	55
17.2	Administrative procedures	55
17.3	Ethics and Good Clinical Practice	55
APPEND	DIX A - STUDY SCHEDULE	56
APPEND	DIX B- Supplemental TRANSPLANTATION /OTHER APPENDICES	58
APPEND	DIX C – Supplemental TRANSPLANTATION	59
REFEREI	NCE LIST	60

CONFIDENTIAL	Clinical Protocol	DATE	Р	age
		9Dec2019		T
	mented Disc Regeneration in the Treatment of the or without Intervertebral Disc Herniation –	WRITER TG, DB, PW	NO. 9	REV 6

STUDY CONTACTS

Sponsor: Vivex Biologics, Inc.

[name]

[contact]

Medical Monitor: H. [name]

Chief Medical Officer Vivex Biologics, Inc.

[contact]

Clinical Representative: [name]

Clinical Program Manager

Vivex Biologics, Inc.

[contact]

Principal Investigator: [name]

[name]

[name]

[name] [contact]

CONFIDENTIAL	Clinical Protocol	DATE 9Dec2019	P	age
	mented Disc Regeneration in the T reatment of the or without Intervertebral Disc Herniation –	WRITER TG, DB, PW	NO. 10	REV 6

PROTOCOL SYNOPSIS

Title	Viable Allograft Supplemented Disc Regeneration in the Treatment of Patients with Low Back Pain with or without Intervertebral Disc Herniation – VAST Trial
Objective	To evaluate the safety and efficacy of viable allograft transplantation for the treatment of patients with symptomatic disc degeneration and tissue loss
Study Design	Multi-center, prospective, parallel, triple arm study to assess patients who participated in the VAST trial and receiving either viable allograft, saline, or allograft after cross-over. These patients will be evaluated at baseline, injection, 6 months, and 12 months. Subjects will then have an option for a 24 months and 36 months extension after their index procedures. Patients who received saline or active allograft in the VAST study, will be allowed to receive viable allograft and followed for an additional 12 and 24 months after that election. These subjects will need to meet initial inclusion/exclusion criteria again before another injection.

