7 EFFICACY AND SAFETY MEASUREMENTS

7.1 Study Procedure

In the scope of routine procedures of the investigating centers, each patient with the given indication will undergo treatment as defined in the study. Besides the investigator's standard of care procedure, after being informed about and giving consent to the screening for potential participation in the study, the following evaluations will be performed for each patient.

7.1.1 Screening Phase Day -14 to Day 0 or VS1:

Potential subjects will be identified and will provide written informed consent for the entire study before undergoing screening and study specific procedures. The investigator or designee will check the inclusion and exclusion criteria and collect the patient data and medical history. A physical examination will be performed and all concomitant diseases and medication will be documented. The scores/scales defined as ODI, VASPI, and SF-36 will be completed by the subject, and assisted by the physician or physician designate (as needed), and a "baseline" MRI, X-ray, and laboratory evaluation will be performed. All required assessments are outlined in Appendix A. VS1 may require multiple clinic visits during this 14-day eligibility screening period. Patients will have had disc pain for a minimum of 6 months to be included. Ineligible subjects should be identified early in the process and prior to completing an MRI and X-ray. MRI and X-ray images up to 6 months prior to treatment are acceptable.

7.1.2 Active Phase Day 0 or VA1:

The Baseline Visit (Day 0) of the Active Phase will occur for subjects that are consented and meet eligibility criteria. MRI/X-ray images performed up to 6 months prior to Day 0 are acceptable to be used for eligibility criteria assessment. Subjects who continue to meet all inclusion and exclusion criteria will need to have all baseline questionnaires, scores/scales, and additional assessments completed, including concomitant diseases, medication information and resource utilization as outlined in Appendix A. All subjects randomized to the allograft or placebo treatment groups will have the patency of the affected disc confirmed. Hereafter, these subjects will undergo preparation for receiving the supplemental allograft treatment or randomized to placebo treatment (saline), or randomized to conservative care treatment.

CONFIDENTIAL	Clinical Protocol	DATE	P	age

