8.5 Assessments

- Informed Consent will be obtained between Screening Day -14 and Active Day 0, prior to any study procedures being performed. The addendum for optional long term follow up will be collected before procedure and questionnaires are performed.
- An assessment of eligibility using the inclusion and exclusion criteria will be conducted starting at Day -14 of the Screening Phase. Prior to randomization at Day 0 of the Screening Phase, eligible subjects must meet all inclusion criteria and no exclusion criteria for the Active Phase. This will also be assessed after the ICF addendum for long term follow up is collected to determine if the subject is still eligible.
- Medical History and Patient Demographics will be recorded during the Screening Phase.
- An abbreviated Physical Examination will be done in the Screening Phase within the 2 weeks prior to transplant, as well as at Month 6, and 12, and at 3 months for the subjects randomized to continue conservative care. This will be done for subjects completing the placebo crossover injection as well.
- Resource utilization data (lost time from work, number and kind of previous surgeries, duration of complaints (preoperatively), duration of rehabilitation, complications, additional physician visits, etc.), will be obtained during the Screening Phase as a baseline to similar data obtained during the Active Phase at Months 6, and 12. This will also be collected during the long term follow up visits of 24 and 36 months.
- Physicians clinical assessments will be collected in the Screening and in the 2 weeks prior to transplant, and in the Active Phase at Months 6, and 12, and in the conservative

CONFIDENTIAL	Clinical Protocol	DATE	Р	age
		9Dec2019		
	mented Disc Regeneration in the $\underline{\mathbf{T}}$ reatment of th or without Intervertebral Disc Herniation –	WRITER TG, DB, PW	NO. 37	REV 6

- care patients at 3, 6, and 12 months. A neurological exam will be completed before placebo crossover additionally.
- Patient self-assessments including VASPI, ODI, and SF-36 will be collected at every scheduled clinic visit. VASPI, ODI, and SF-36 will be collected in person at 24 months and at the 36 month interval, these questionnaires can be performed over the phone during optional long term follow up.

CONFIDENTIAL	Clinical Protocol	DATE	Р	age
		9Dec2019		

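### Protocol 7.1.4 uses the same 3-month scores to trigger crossover and as the new baseline, which builds a spurious improvement into change counted from the crossover injection

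*Protocol*

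**What the plan says.** The crossover rule is in Protocol 7.1.4 and is repeated in part in 8.4. "Subjects who have experienced a significant decline in condition defined as a 10% increase in pain by VASPI, or a 9-point increase in ODI" are offered allograft. Others may be offered it at physician discretion. Three further statements in 7.1.4 matter here:

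- The baseline: "All assessments done at this 3 months follow-up visit will be considered as the new baseline assessments".
- The timing: "The crossover allograft treatment can occur at any time period after the 3-month follow-up visit".
- The injection takes place at a newly scheduled visit that counts as a new Active Phase Day 0, with follow-up 6 and 12 months after the injection. Appendix A, footnote c, labels that visit VA1.

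On whether ODI and VASPI are scored at Day 0, section 8.5 says that patient self-assessments "including VASPI, ODI, and SF-36 will be collected at every scheduled clinic visit". The VA1 column of Appendix A is blank for ODI, VASPI and SF-36. Section 7.1.2 says that subjects at Day 0 "will need to have all baseline questionnaires, scores/scales, and additional assessments completed", but that sentence goes on to refer to Appendix A for the detail.

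The synopsis describes the patients assessed as "receiving either viable allograft, saline, or allograft after cross-over".

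The SAP analyzes pre-post differences (9.1) and does not say which score is the pre value for a crossover. The primary mITT analysis is by randomized arm (6.2). Section 11.1 repeats the primary endpoints by treatment received. No separate crossover group is planned.

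**The concern.** An observed rise of 9 points is partly true change and partly error: a low reading at enrollment, a high reading at month 3, or both. Selecting patients on that rise selects positive error in the 3-month score. If that score is then the starting point, the error drops out at the next visit and is counted as improvement after allograft. An inert injection would show the same fall.

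What is at stake is first any before-and-after result reported for the crossovers, where the bias is undiluted. Second, because the SAP leaves the baseline open, an analyst could carry the 7.1.4 baseline into the by-treatment-received analysis or into the as-randomized analysis. The two choices push in opposite directions.

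**Working it through.** **Inputs from the documents.** ODI SD 15.5 and reliability 0.75 to 0.91 (Protocol 13.3, SAP 4); ODI trigger +9 (Protocol 7.1.4); entry at ODI of at least 40 (Protocol 8.1); arms of 140, 40 and 40 (SAP 4).

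**Assumptions.** Normal errors, independent between visits. For the version with entry selection, the source population has an observed mean ODI of 40 to 50.

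**1. The plan's own figure.** Error SD = SD × √(1 − reliability). 15.5 × √0.25 = 7.75, which is the measurement error stated in Protocol 13.3. At the other end, 15.5 × √0.09 = 4.65.

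**2. Chance rise, no true change, no entry selection.** SD of a difference = error SD × √2. With z = 9 / SD of difference, P(trigger) = 1 − Φ(z), and the mean rise given trigger = SD of difference × φ(z) / (1 − Φ(z)). The two errors contribute equally, so half of the mean rise is error in the 3-month score.

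| | Reliability 0.75 | Reliability 0.91 |
|---|---|---|
| SD of difference | 10.96 | 6.58 |
| P(trigger) | 0.206 (8.2 of 40) | 0.086 (3.4 of 40) |
| Mean rise if triggered | 15.17 | 12.02 |
| Spurious improvement from the 3-month baseline | 7.58 | 6.01 |

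**3. With entry selection.** Requiring an observed ODI of at least 40 at entry, numerical integration for source means of 40, 45 and 50 gives:

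- Reliability 0.75: P = 0.125, 0.142, 0.157; spurious improvement 9.45, 9.04, 8.68.
- Reliability 0.91: P = 0.059, 0.065, 0.070; spurious improvement 6.65, 6.51, 6.39.

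In this model every enrolled patient already carries a mean entry error of 0.6 to 3.1 points. The excess over an ordinary enrolled patient is therefore 5.5 to 7.0 points.

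**4. With a true 9-point rise.** Now z = 0, so the 3-month error given trigger = 0.5 × SD of difference × 0.798, which is 4.37 and 2.62. With entry selection it is 5.1 to 5.7 and 2.9 to 3.0.

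**5. SAP 11.1, if it used the 7.1.4 baseline and only truly stable controls triggered.** Shift of the allograft mean = 40 × P × error / (140 + 40 × P). Closed form: 8.23 × 7.58 / 148.23 = 0.42 and 3.42 × 6.01 / 143.42 = 0.14. With entry selection: 0.11 to 0.37.

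**6. As-randomized mITT, if it used the 7.1.4 baseline.** Moving a triggered patient from the screening score to the 3-month score changes the pre value by the whole observed rise, so the conservative-care mean shifts by P × mean rise. Closed form: 0.206 × 15.17 = 3.1 and 0.086 × 12.02 = 1.0. With entry selection the mean rise is 14.2 to 14.5 at reliability 0.75 and about 11.8 to 11.9 at 0.91. That gives from 0.059 × 11.8 = 0.7 to 0.157 × 14.5 = 2.3. The shift favors conservative care, and it is larger if controls truly decline.

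**7. A fresh Day 0 score as baseline.** With independent errors, simulation gives a spurious change of −0.03 to +0.04 points. If the month-3 and Day 0 errors have correlation ρ, a share ρ of the 3-month error remains. For ρ of 0.3 to 0.5 (assumed) and no true change, that is 0.3 × 6.39 = 1.9 to 0.5 × 9.45 = 4.7 points.

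VASPI is not computed, because the documents give no SD or reliability for it.

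**The case against.** The strongest reply is that no planned analysis is shown to be affected. The SAP has no crossover estimate, its primary analysis is as randomized, and neither document says that the 7.1.4 baseline enters any test. Even in SAP 11.1, already a non-randomized sensitivity analysis, the shift is 0.1 to 0.4 points against a design difference of 9. This stands, and it limits the point. It does not remove it: the synopsis names crossover patients among those assessed, 7.1.4 fixes a baseline for them, and the SAP leaves its use open.

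Three further objections hold in part.

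- The 6 to 9.5 points apply to patients triggered by ODI with no true change. Those who cross over by VASPI or by discretion are less selected on ODI, and the documents give no expected mix of routes.
- A Day 0 score removes the fall only if errors at the two visits are independent. The documents give no between-visit correlation, and 7.1.4 sets no minimum interval.
- A reader might infer that several sections demand Day 0 scores against Appendix A. Only 8.5 clearly does. Section 7.1.2 defers to Appendix A and can mean completed by Day 0. The synopsis line "These patients will be evaluated at baseline, injection, 6 months, and 12 months" names no questionnaire.

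A reader might also infer that the primary result is tilted toward allograft. The documents do not support that. Crossovers stay in the conservative-care arm in the mITT analysis, so using this baseline there would credit conservative care. Allograft versus saline as randomized involves no crossover patient.

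**Conclusion.** The concern holds in a limited form. Section 7.1.4, followed as written, overstates ODI change counted from crossover by about 6 to 9.5 points for ODI-triggered patients with no true change, and by about 2.6 to 5.7 points with a true 9-point rise. For comparison, Protocol 13.3 cites a minimum important difference of 6 points. These figures rest on the protocol's SD and reliability, normal independent errors and, for the upper values, an assumed source mean of 40 to 50.

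The consequence for planned analyses is conditional on which baseline is used, and the two possible shifts run in opposite directions: toward allograft in SAP 11.1 and toward conservative care in mITT. They are shifts in means, whereas the planned tests use ranks, so they indicate direction and scale and not a change in p-value. The direct document conflict on Day 0 scores is between 8.5 and the VA1 column of Appendix A.

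**What to change.** 1. **Protocol.** Replace the baseline sentence in 7.1.4 so that ODI and VASPI taken at the crossover Day 0 visit, before injection, are the baseline for results counted from crossover. Mark both at VA1 in Appendix A for crossovers, which also settles the conflict with 8.5 for these patients. This removes the built-in fall if errors at the two visits are independent and reduces it otherwise.
2. **SAP.** State that the as-randomized mITT analysis keeps the screening baseline for crossovers, and that 11.1 uses the crossover Day 0 baseline.

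The screening score is not a substitute in step 1. The trigger also selects low enrollment readings, so with no true change it would show an apparent worsening of about 4.8 to 5.9 points (simulation with entry selection, source mean 40 to 50).

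The cost is two short questionnaires at an existing visit, for crossovers only, plus one protocol sentence, one Appendix A entry and two SAP sentences. The mITT sentence needs no new data. The triggers, and so who is offered crossover, do not change.
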